### 7.1 **Primary Objective**

The primary objective of this study is

• To assess the safety and tolerability of a twice daily, 7-day repeat topical doses of Nu-3 in adult male and female patients with chronically infected diabetic ulcer.

### 7.2 Secondary Objectives

The secondary objectives of the study are:

- To assess the clinical and microbiological response to bisphosphocinTM Nu-3.
- To support determination of the appropriate dose range of Nu-3 to be employed in future clinical studies.

#### 8 STUDY DESIGN

### 8.1 **Overall Study Design**

This study is a Phase 1/2a prospective, multi-center, blinded, randomized (with respect to placebo), dose escalation, twice daily for 7 consecutive days study of Nu-3 solution administered topically in patients with chronic diabetic foot ulcer.

#### 8.2 **Number of Centers**

This study will be conducted at two to four investigative site.

#### 8.3 Cohorts

The dose of Nu-3 administered will be escalated in five planned sequential cohorts, with 10 subjects in each cohort, to be administered Placebo (0.9% saline) or Nu-3 doses of 0.1% solution of BisphosphocinTM Nu-3 in 0.9% saline (w/v) (Cohort 1), 1% solution of BisphosphocinTM Nu-3 in 0.9% saline (w/v) (Cohort 2), 2% solution of BisphosphocinTM Nu-3 in 0.9% saline (w/v) (Cohort 4), 10% solution of BisphosphocinTM Nu-3 in 0.9% saline (w/v) (Cohort 5) at twice daily for 7 consecutive days.

Additional cohorts may be enrolled, if needed, as provided by protocol.

### 8.4 Placebo Control

In each Cohort, 8 subjects will be randomized to receive Nu-3, and 2 subjects will be randomized to receive Placebo.

### 8.5 Number of Subjects

Approximately 50 subjects will be enrolled, of which approximately 40 will be exposed to Nu-3. Numbers may vary due to replacement of subjects, addition of cohorts as permitted by protocol, or stopping of study.

### 8.6 Study Visits

Subjects will have 5 nominally scheduled study visits: Screening (Day -7 to -4 hours), Single Dose Visit (Day 1), Safety Review and Multiple Dose Visit (Day 2), Safety Review Visit (Day  $9 \pm 1$  day) and Final Visit (Day  $15 \pm 2$  days). Additional visits for screening procedures and/or follow-up (e.g., in follow-up of Adverse Events) may be necessary.

### 8.7 **Study Duration**

From consent and screening through final visit, a subject's duration of participation may vary between approximately 2 and 3 weeks. No individual subject will be randomized more than once in this study.

### 8.8 **Dose Selection and Rationale**

While mechanisms of the demonstrated therapeutic effect of Nu-3 in the animal models, and of the proposed therapeutic effect in humans, are unknown, structural characteristics of Nu-3 have not suggested homology with any genetically encoded human biological molecule. There is no known suggestion of ligand-receptor specificity, and in particular no suggestion of immune system effect at the proposed doses. Preclinical studies have not suggested a species specificity for any pharmacodynamic effect.

Accordingly, Nu-3 is not regarded as a higher-risk agent, and a conventional method for determination of maximum safe starting dose is considered appropriate for this first-in-human study.

#### 8.9 First Dose Plan

The dosing schedule for all cohorts is intended to minimize potential risk to subjects' safety. It is known that the types, severities, time courses and pharmacokinetic correlates of adverse effects observed in preclinical studies are not necessarily predictive of experience in human subjects, at any dose. This plan further recognizes that major acute toxicities of pharmaceuticals in human subjects may on rare occasions not be predicted by preclinical

experience, warranting additional caution in administering first doses to humans. As such caution has been advised in particular regarding biopharmaceuticals, it is noted that Nu-3 is not categorized as a biopharmaceutical. A traditional risk-reduction strategy has been to apply large safety factors (divisors of human equivalent doses corresponding to NOAELs in appropriate animal toxicology models) in determining the Maximum Safe Starting Dose for first-in-human study. A further risk-reduction strategy, adopted here, is to separate first and second exposures more widely in time than has been typical study procedures.

Preclinical experience suggests that possible adverse effects after a single dose topical exposure to NU-3 would be unlikely. Accordingly, the dose plan is as follows:

- Qualified patients for all Cohorts are screened from Day -7 to -4 hours. Patients understand (disclosed in informed consent) that their qualification for enrollment is not finalized until the time of enrollment. They understand that their order of enrollment is randomly determined.
- On Day -7 to -4 hours, baseline procedures are performed (demographics and medical history, and limited physical examination per protocol, urine pregnancy test (if applicable), baseline laboratory tests (blood chemistries, hematology, coagulation profile, and urinalysis), and baseline subject disease assessments).
- On Day 1, the patients is randomized and dosed to either Nu-3 or Placebo.
- On the next following day, Day 2, if the Investigator observes no dose-limiting toxicity (Section 8.10.6) in the patient dosed on Day 1, the Investigator will distribute the investigational product kit and instructed to apply the product twice daily for one (1) week (7 days).
- If the Investigator observes a suggestion of dose-limiting toxicity, the procedure specified in Section 8.10.3 is followed.

### 8.10 **Safety Review**

### 8.10.1 **Safety Review Committee**

Membership of the Safety Review Committee includes the Sponsor's designated Medical Monitor, the Medical Director of the CRO, Medical Director of Lakewood Amedex, and other member(s) as deemed appropriate by Sponsor.

### 8.10.2 **Safety Review Procedure**

Decisions regarding dose escalation and/or modification (including option of next cohort repeating at same dose, or doses intermediate to or reduced from those planned per protocol) are based upon review by the Safety Review Committee of safety data to the date of the Safety Review Visit (including data at least through the Day 8 Safety Review Visit) for the current cohort and safety data of the preceding cohorts to the date of the Safety Review Visit.

- Safety Review meeting may be conducted by teleconference.
- Decisions of the Safety Review Committee must be unanimous among the members participating in the review and are recorded in meeting minutes.
- Draft minutes of Safety Review Committee meetings are reviewed by all members who attended. Proposed changes are reviewed by all members who attended. Final draft of minutes is approved by consensus.
- Individual members' approvals of final draft minutes are documented to study regulatory file.
- Final draft of minutes is placed in study regulatory file and provided to IRB.

### 8.10.3 Cohort 1 Day 1a Experience

If a Subject dosed on Day 1 of Cohort 1 experiences any therapeutic adverse event around the wound area:

- Further dosing of Cohort 1 is suspended.
- The Safety Review Committee meets to consider available safety data.
- The Safety Review Committee decides and documents rationale for further course of action, which may include resumption of study conduct.

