#### 8.10.5 **Decision Criteria**

8.10.5.1 Stopping of Dose Administration and/or Escalation

Further study drug dose administration or escalation will be stopped:

- 1. by Sponsor, for any reason at any time;
- 2. by Principal Investigator or Safety Review Committee, if subjects' safety is considered to be at unacceptable risk;
- 3. by Safety Review Committee, according to these criteria:
  - If 2 or more of the Nu-3-treated subjects in a cohort experience a DLT, dose escalation is stopped;
  - If 1 of the Nu-3-treated subjects experiences a DLT, the cohort is expanded to include 4 additional subjects (Nu-3:Placebo ratio of 3:1); and
  - If 2 or more of the Nu-3-treated subjects in the expanded cohort (of 8+4=12 subjects) experience a DLT, dose escalation is stopped;
  - If only 1 of the Nu-3-treated subjects in the expanded cohort experiences a DLT (i.e., no additional subjects experience a DLT following cohort expansion), stopping of dose escalation is not required.

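### Protocol 8.9 sends a suspected Day 1 DLT in any cohort to 8.10.3, but 8.10.3 suspends dosing in Cohort 1 only, so whether Cohorts 2–5 pause is unclear

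*Protocol*

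**What the plan says.** Protocol section 8.9 is written for the whole trial: "The dosing schedule for all cohorts is intended to minimize potential risk to subjects' safety". The Day 2 kit is handed over only "if the Investigator observes no dose-limiting toxicity (Section 8.10.6) in the patient dosed on Day 1". Otherwise, "If the Investigator observes a suggestion of dose-limiting toxicity, the procedure specified in Section 8.10.3 is followed". No cohort limit is attached to that referral.

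Section 8.10.3 is headed for Cohort 1. It applies on this condition: "If a Subject dosed on Day 1 of Cohort 1 experiences any therapeutic adverse event around the wound area". Three steps follow:

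1. "Further dosing of Cohort 1 is suspended"
2. "The Safety Review Committee meets to consider available safety data"
3. "The Safety Review Committee decides and documents rationale for further course of action, which may include resumption of study conduct"

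Section 8.10.5.2 defines a DLT as a CTCAE Grade 2 or higher event judged at least possibly related to study drug, at any body site. Section 8.10.5.1 covers every cohort. It allows stops by the sponsor for any reason and "by Principal Investigator or Safety Review Committee, if subjects' safety is considered to be at unacceptable risk". It also has DLT counts: one DLT expands the cohort, and two or more stop escalation.

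**The concern.** The referral and the procedure do not match. Section 8.9 points every cohort to 8.10.3, while both the condition and the suspension step there name only the first cohort. The triggers differ as well: 8.9 uses a suspected DLT at any site, and 8.10.3 uses an event at the wound.

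This is a first-in-human escalation, and the only explicit pause sits at the lowest dose, 0.1%. The patch test described in Protocol section 6 used 2% Nu-3, which irritated abraded skin more than saline did. Cohorts 4 and 5 apply 5% and 10% to open ulcers. After a suspected Day 1 DLT at those doses, the affected patient is held at the Day 2 check, but a site cannot tell from the text whether it may go on dosing the rest of the cohort before the committee decides.

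**Working it through.** There is no planned figure to reproduce. The check sets the provisions side by side and then counts who is covered.

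**Step 1: referral against procedure**

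| | Section 8.9 | Section 8.10.3 |
|---|---|---|
| Cohorts | All | Cohort 1 |
| Trigger | Suggestion of DLT after Day 1 | Therapeutic adverse event near the wound, Day 1 |
| Dosing pause | By reference to 8.10.3 | Cohort 1 |
| Committee meets and decides | By reference to 8.10.3 | Yes, no cohort named |

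**Step 2: two readings**

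- *Literal.* The 8.10.3 condition must be met. It cannot be met in Cohorts 2 to 5, and a systemic DLT does not meet it even in Cohort 1.
- *Generous.* Section 8.9 supplies the trigger and 8.10.3 supplies the steps. Steps 2 and 3 name no cohort, so committee review applies everywhere. Step 1 still names Cohort 1, so the text does not say whether the current cohort stops.

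**Step 3: does another provision pause the cohort?**

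| Provision (Protocol) | What it does | Automatic cohort pause? |
|---|---|---|
| 8.9, Day 2 check | Withholds the kit from one patient | No |
| 12.4, ulcer examination | Decides whether one patient continues | No |
| 9.2, withdrawal | Removes one patient | No |
| 8.10.5.1 items 1–2; section 20 | Stop on sponsor, investigator or committee judgement | No |
| 8.10.5.1 item 3, one DLT | Expands the cohort | No |
| 8.10.5.1 item 3, two or more DLTs | Stops escalation | No |
| 8.11, later cohorts | Sets dose, numbers and spacing | No |

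**Step 4: scope**

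Inputs: five cohorts (8.3), eight Nu-3 subjects in each (8.4, 10.2), one Day 1 application and then twice daily for 7 days (10.2). SAP section 3 lists three cohorts of ten randomised 4:1, so again eight on Nu-3 in each.

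- Nu-3 subjects outside Cohort 1, Protocol: 4 × 8 = 32 of 5 × 8 = 40; 32 / 40 = 80%.
- Nu-3 subjects outside Cohort 1, SAP: 2 × 8 = 16 of 3 × 8 = 24; 16 / 24 = 67%.
- Upper bound on further Nu-3 subjects dosed after a DLT in the first one in a cohort: 8 − 1 = 7. Expansion subjects are left out because they enter only under a rule the committee applies.
- Scheduled applications per subject: 1 + (2 × 7) = 15, so a pause can still matter after the Day 1 doses have been given.

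**Step 5: nearby references**

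Section 8.9 cites 8.10.6 for DLT. No such section exists, and the definition is in 8.10.5.2. Section 8.10.5.3 cites 8.10.4 for the stopping criteria, but 8.10.4 covers unblinding and the criteria are in 8.10.5.1. Both are clerical and add no weight to the main point.

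**The case against.** The best defence is that a cross-reference imports a procedure and adapts it. Section 8.9 gives its own trigger with no site limit, cohorts run in sequence, and the mention of resuming the study implies that something was paused. A sensible reader would then take Cohort 1 to mean the cohort now being dosed. This does answer the systemic-DLT point on the generous reading, and it puts committee review in every cohort. It does not settle the pause, because the only suspension sentence has to be reworded before it applies.

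The opposite defence is that suspension was meant for the first cohort only, since later cohorts have their own section, 8.11, without such a step. That is possible, but it conflicts with the unrestricted referral in 8.9, so the text would still need correcting.

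Other safeguards are real. Under 8.10.5.1 a stop follows once risk is judged unacceptable; what is discretionary is the judgement. The three-cohort protocol texts in the same file also contain study-wide suspension rules (sections 6.4.2 and 7.3.1). Those texts appear to be other versions of the protocol. The five-cohort text does not carry the rules over, and the Grade 3 or 4 rule in 7.3.1 would not reach a Grade 2, possibly related DLT.

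It is also fair that the figures are not risk estimates. The bound of 7 assumes that the first Nu-3 subject is the one affected, that the whole cohort follows, and that no one uses a discretionary stop.

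**Conclusion.** The concern holds as an internal inconsistency that should be corrected. Followed literally in Cohorts 2 to 5, section 8.10.3 pauses nothing. Read generously, it secures committee review and leaves the pause unstated. The gap is the automatic, cohort-level suspension; it is not an absence of safeguards. Its reach is 80% of planned Nu-3 subjects under the Protocol, or 67% under the SAP's three cohorts. These shares assume full enrolment at eight Nu-3 subjects per cohort. Confidence in the textual finding is high. The documents give no DLT rate, so the practical consequence cannot be quantified further. Spacing between successive subjects is a separate matter and is not part of this point.

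**What to change.** Amend the Protocol as follows.

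- Retitle 8.10.3 to cover Day 1 experience in all cohorts.
- Give it two triggers: a suspected DLT (as defined in 8.10.5.2) in a subject dosed on Day 1 of any cohort, or the existing wound-area trigger for Cohort 1.
- State that on either trigger further dosing of the current cohort is suspended, the Safety Review Committee meets, and it documents its decision before dosing resumes.
- In 8.9, change the DLT reference from 8.10.6 to 8.10.5.2. In 8.10.5.3, change 8.10.4 to 8.10.5.1.

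While drafting, the sponsor should also say whether the suspension covers subjects already applying product at home, and how it fits with the one-DLT expansion rule in 8.10.5.1.

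The drafting cost is small. If the suspension was meant for Cohort 1 only, this is a substantive new rule: one suspected Grade 2, possibly related event would pause the current cohort until the committee reaches the unanimous decision that 8.10.2 requires. The downside is possible short enrolment pauses in later cohorts, limited by the teleconference option in 8.10.2. If the sponsor prefers to keep the suspension to Cohort 1, section 8.9 must say so and state what sites do instead in Cohorts 2 to 5.

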### 8.10.4 Unblinding for Safety Review

If the Safety Review Committee decides that unblinding of dose randomization is necessary for decision regarding continued dosing and/or dose escalation, the unblinding is done in a manner that minimizes the extent of unblinding and of its potential effects on assessments of adverse events. This action is documented in the minutes of the Safety Review Committee meeting.

#### 8.10.5 **Decision Criteria**

8.10.5.1 Stopping of Dose Administration and/or Escalation

Further study drug dose administration or escalation will be stopped:

- 1. by Sponsor, for any reason at any time;
- 2. by Principal Investigator or Safety Review Committee, if subjects' safety is considered to be at unacceptable risk;
- 3. by Safety Review Committee, according to these criteria:
  - If 2 or more of the Nu-3-treated subjects in a cohort experience a DLT, dose escalation is stopped;
  - If 1 of the Nu-3-treated subjects experiences a DLT, the cohort is expanded to include 4 additional subjects (Nu-3:Placebo ratio of 3:1); and
  - If 2 or more of the Nu-3-treated subjects in the expanded cohort (of 8+4=12 subjects) experience a DLT, dose escalation is stopped;
  - If only 1 of the Nu-3-treated subjects in the expanded cohort experiences a DLT (i.e., no additional subjects experience a DLT following cohort expansion), stopping of dose escalation is not required.

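### No DLT count pauses dosing at the current level, the suspected-DLT procedure is written only for Cohort 1 wound-area events, and non-serious DLTs have no reporting deadline

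*Protocol*

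**What the plan says.** This point concerns the five-cohort protocol text.

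- **Stopping rule (8.10.5.1).** The lead-in covers both actions: "Further study drug dose administration or escalation will be stopped". The sponsor may stop for any reason, and the Principal Investigator or committee may stop for unacceptable risk. The DLT counts follow as a third item. Two or more: "If 2 or more of the Nu-3-treated subjects in a cohort experience a DLT, dose escalation is stopped". Exactly one: four subjects are added at 3:1. Two or more after expansion: escalation stops. Still one: escalation need not stop.
- **DLT definition (8.10.5.2).** Grade 2 or higher and at least possibly related in the Investigator's view. Seriousness is not required and no time window is given.
- **Day 2 check (8.9, for all cohorts).** The home kit is given out "if the Investigator observes no dose-limiting toxicity (Section 8.10.6) in the patient dosed on Day 1". Otherwise: "If the Investigator observes a suggestion of dose-limiting toxicity, the procedure specified in Section 8.10.3 is followed".
- **That procedure (8.10.3, headed for Cohort 1 Day 1a).** Trigger: "If a Subject dosed on Day 1 of Cohort 1 experiences any therapeutic adverse event around the wound area". Action: "Further dosing of Cohort 1 is suspended"; the committee then meets and decides.
- **Reporting (13.4).** SAEs are telephoned at once to the Medical Monitor or Safety Officer. Other AEs are recorded, with no time limit for telling either the Medical Monitor or the committee.
- **Oversight.** The committee is the sponsor's "designated Medical Monitor, the Medical Director of the CRO, Medical Director of Lakewood Amedex", plus others the sponsor may add (8.10.1). Its scheduled review comes after each cohort (16.3). The SAP (section 3) repeats that review and adds no DLT or pause rule.
- **Sites.** "This study will be conducted at two to four investigative site" (8.2).

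**The concern.** The counts are made over a whole cohort, and the cohort may be spread over several sites. A site that sees one DLT cannot know that another site has seen one, and nothing requires either site to tell the committee promptly if the events are not serious. If the plan is followed exactly, subjects can keep applying the product, and new subjects can start, at a level with DLTs before the committee that applies the count need hear of them. That level could later be placed above the maximum tolerated dose under 8.10.5.3. With exactly one Nu-3 DLT the rule adds subjects at that level and states no pause.

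The explicit suspension is attached to the 0.1% cohort. Cohorts 2 to 5 use 1% to 10%, which is 10 to 100 times that concentration, in what section 8.8 calls a first-in-human study.

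**Working it through.** The plan gives no operating characteristic for the DLT rule, so there is no figure to reproduce. The point rests mainly on setting the sections side by side.

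**1. What an event triggers on the wording**

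| Suspected DLT | Cohort 1 | Cohorts 2–5 |
|---|---|---|
| Day 1–2, at the wound | 8.9 withholds the kit; 8.10.3 suspends Cohort 1 | 8.9 withholds the kit and points to 8.10.3, which names and suspends only Cohort 1 |
| Day 1–2, away from the wound | Kit withheld; outside the 8.10.3 trigger | Same |
| Home phase, at the wound | Arguably 8.10.3, since its trigger dates the subject's dosing and not the event; the heading suggests otherwise | Outside the 8.10.3 wording |
| Home phase, away from the wound | Outside the 8.10.3 wording | Outside the 8.10.3 wording |

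The DLT reference in 8.9 is also wrong: there is no section 8.10.6, and the definition is in 8.10.5.2.

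**2. Exposure after the Day 2 check** (10.2, 12.4)

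1 application on Day 1 + 2 × 7 = 15. Fourteen follow the check: one observed in clinic and 13 at home. The next scheduled AE assessment is Day 9 (12.9), so home-phase events surface earlier only if subjects report them.

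**3. Reporting load of the fix** (8 Nu-3 and 2 placebo subjects per cohort, 8.4)

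The DLT rates p (Nu-3) and q (placebo) are assumptions. Expected subjects with a suspected DLT = 8p + 2q.
- Low end, p = 0.05, q = 0.10: 0.4 + 0.2 = 0.6
- High end, p = 0.50, q = 0.30: 4.0 + 0.6 = 4.6

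**4. The optional automatic pause only**

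Assume independent subjects, and let T be the position of the Nu-3 subject with the second DLT: P(T = t) = (t − 1)p²(1 − p)^(t−2), t = 2 to 8. Subjects not started = E[max(8 − T − L, 0)], where L is the number of further Nu-3 subjects started before the pause takes effect.

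| p | P(2 or more of 8) | Not started, L = 0 | Not started, L = 2 |
|---|---|---|---|
| 0.05 | 0.057 | 0.12 | 0.05 |
| 0.10 | 0.187 | 0.44 | 0.17 |
| 0.20 | 0.497 | 1.36 | 0.59 |
| 0.30 | 0.745 | 2.38 | 1.13 |

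These are averages over all cohorts. L = 0 is the best case. If all ten subjects start at the 20-minute minimum in 8.11 (9 × 20 = 180 minutes), the gain in subjects not started is zero and only continuing home dosing could be halted.

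If suspected DLTs are counted in either arm, the chance of a pause with fewer than two Nu-3 DLTs is 8p(1 − p)⁷[1 − (1 − q)²] + (1 − p)⁸q². Over p = 0.05 to 0.50 this is about 1–8% at q = 0.10, 1–16% at q = 0.20 and 2–23% at q = 0.30.

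Two limits apply. The benefit figures count Nu-3 DLTs only, while the pause would count either arm, so the two sets cannot be netted off. The model also stops at the first 8 Nu-3 subjects and ignores the expansion, which exactly one DLT triggers with probability 0.279, 0.383, 0.336 and 0.198 at the four rates.

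**The case against.** The strongest reply is that the protocol already intends a pause. Section 8.9 opens with all cohorts, and its last bullet carries no Day 2 limit. The procedure it names is to suspend, convene and decide. On that reading the Cohort 1 label is a leftover, and a committee meeting implies that someone told the committee. Within Cohort 1, every subject is dosed on Day 1, so a home-phase wound-area event literally meets the 8.10.3 trigger.

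Much of this stands. A reader might infer that no cohort has any automatic pause after Day 2; the documents do not support that. They leave Cohort 1 wound-area events arguably covered and the rest unclear. The reply does not supply an action for Cohorts 2 to 5, because the only suspension written there is of Cohort 1. It also does not bring DLTs away from the wound within 8.10.3.

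A reader might also infer that non-serious events stay at the site. They do not: data go straight into an electronic system (18.2), the sponsor or CRO reviews records at regular intervals (19), and the Medical Monitor is told of medications taken (11.2). None of these routes has a deadline.

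Local safeguards are real. The investigator judges relatedness and so knows of the event, is on call (13.2), must withdraw a subject for an AE judged significant (9.2), and may stop dosing or the study (8.10.5.1, 20). Subjects are told to report AEs (13.4), and the committee may lengthen the dosing interval (8.11). These act on one subject or depend on judgement, and none ensures that other sites or the committee hear promptly.

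Finally, Grade 2 is a low threshold for an automatic pause. That is fair, and it is why the pause is left optional.

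**Conclusion.** The point holds and should be fixed. It is a cheap safety clarification rather than a flaw in the analysis. Three things follow from the text without any assumed rate: no DLT count pauses dosing at the current level; the route from 8.9 to 8.10.3 gives no workable action for DLTs in Cohorts 2 to 5 or away from the wound; and non-serious DLTs have no deadline for reaching the Medical Monitor or the committee.

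The size of the patient benefit from the core fix is not quantified. A reader might take the subjects-not-started figures as its justification, but they describe only the optional pause, rest on assumed DLT rates and independence, and fall to zero if the whole cohort starts before the second DLT is known. Confidence is medium, because the intended scope of 8.10.3 is a matter of reading.

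**What to change.** 1. **Section 13.4.** Require any suspected DLT (Grade 2 or higher, at least possibly related), serious or not and in either arm, to be reported to the Medical Monitor by the existing SAE telephone route and passed promptly to the Safety Review Committee.
2. **Section 8.10.3.** Refer to the current cohort in place of Cohort 1 and cover any suspected DLT on any dosing day. Hold the affected subject's dosing and have the committee decide promptly whether to suspend the cohort. Keep the existing Cohort 1 suspension at full strength, so that the change does not reduce a cohort suspension to a hold on one subject.
3. **Section 8.9.** Correct the reference from 8.10.6 to 8.10.5.2.

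**Cost.** A short amendment and site training, with no added subjects or procedures. Expect about 0.6 to 4.6 extra reports and brief committee contacts per cohort at the assumed rates. The contacts are not free: under 8.10.2 committee decisions must be unanimous, and minutes are approved by attendees and sent to the IRB. Some held doses may remove subjects from the per-protocol population, which requires all doses (protocol 16.2, SAP 5.3).

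**Optional.** Pause new randomization and dosing at a level when two suspected DLTs are reported in a cohort, until the committee meets, unblinding only as 8.10.4 allows. The sponsor should weigh this against pauses with fewer than two Nu-3 DLTs, in about 1–8% of cohorts at a placebo DLT rate of 0.10 and 2–23% at 0.30.
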